6.1.6 Route of Administration

Ivermectin 0.5% lotion, is for topical use only. It is not for oral, ophthalmic, or intravaginal use.

6.1.7 Blinding

This is a double-blind study, thus Sponsor, CRO, assessor site staff, study monitors, and subjects will be blinded to the randomization scheme. The packaging of the study drug products will be similar in appearance to make difference in treatment less obvious to the subjects. Blank, opaque diaper labels will be applied to each study tube for maintenance of study blinding. Each tube will be packaged in individualized cartons. Neither the Investigator nor the subject should be able to identify the received treatment. The dispensed investigational product will NOT be opened by the index subject and their family members at the study center.

The blinding code must not be broken except in emergency situations for which the identification of the study treatment of a subject is required by the Investigator to complete a serious adverse event report. In such situations, the Medical Monitor or the Investigator will use the Unblinded Treatment List in order to unblind the treatment for the individual subject. Unblinded information will be held by designated individual(s), and the date and reason for breaking the blind must be recorded.

The Medical Monitor must be contacted by telephone prior to unblinding but no later than 24 hours after unblinding. As the study is blinded, the Investigator should promptly document and explain to the Sponsor any premature unblinding (e.g., accidental unblinding, unblinding due to a serious adverse event) of the investigational product(s).

6.1.8 Duration of Therapy

The study is comprised of three phases: Screening, Treatment, and Follow-Up. The duration of this study is 15 days (+/-3). The Screening Phase is Day -1-0. The Treatment Phase is Day 1. Preferably, screening and treatment will occur on the same day. The Final Study Visit is on day 15 (+/- 3 days) following administration of the study product.

6.1.9 Tracking of Dose and Treatment Compliance

Subject diaries will be distributed and accounted for, along with return of used test tubes. Subjects will fill out their diaries upon treatment application noting the following:

- Time and date of application
- Time and date of removal (washing off the study drug)
- Confirmation that subject disinfected personal clothes, towels, linens and all potentially infected household items
- Confirmation that the entire scalp and hair has been covered by the application

Subjects will return their diaries to the clinical site for compliance review at Follow-up Day 2. The Investigator will verify that the subject complied with the application requirements and disinfection regimen. Both the subject and the study staff will sign off on completed diary. If the subject has missed the treatment application notation, this is considered a protocol deviation and must be reported.

6.2 Study Drug Accountability

The Sponsor will supply sufficient quantities of the study drug for the completion of this study.

The study pharmacist or designated study personnel will maintain a Drug Receipt Log and a Subject Study Drug Accountability Log itemizing all study drug received, dispensed to and returned from each subject during the study. All dispensed tubes must be accounted for, and any discrepancies explained. Study site should contact site Clinical Research Associate (CRA) in case of any dispensing errors or if discrepancies are discovered.

Prior to site closure and at appropriate intervals during the study, site CRA will perform study drug accountability and reconciliation. At the end of the study, the Investigator will retain all the original documentation regarding study drug accountability, return, and copies will be sent to the Sponsor.

All unused and used Study Drug tubes will be returned to the Sponsor or its designee for destruction at the end of the study.

7 Study Procedures and Schedule of Events

7.1 Study Procedures/Evaluations

Basic demographic information, including date of birth, sex, ethnicity, and race will be recorded at the Screening Visit.

Medical history will be collected at the Screening and Baseline Visits. Relevant medical history, alcohol and tobacco history, and past history of head lice will be documented.

All medications (both prescription and nonprescription, including vitamins, herbals, topical, inhaled, and intranasal) taken within 30 days prior to the start of the Study Drug and through the final study visit will be recorded on the appropriate eCRF (using their generic and brand names, if known) with the corresponding indication, start and stop dates. At each study visit, subjects will be asked whether they have started or discontinued any medication since their previous study visit. This includes single use or PRN (as needed) medication use.

Vital signs will be collected at Baseline Visit 1 and Final Study Visit 5. Vital signs will include body temperature, heart rate and blood pressure (systolic and diastolic). Blood pressure and pulse rate will be measured after the subject has been sitting restfully for at least 5 minutes. Any abnormal characteristics of vital signs will be evaluated by the Investigator based on

Protocol Number: MAP-7189

Version 1.3; 28 December 2017

their significance. Any abnormal vital signs will be considered AEs if they require therapeutic medical intervention, and/or if the Investigator considers them to be AEs based on his/her clinical judgement.

Physical examination, including height, weight, and evaluation of organs and systems (General Appearance, Heart/Cardiovascular, Lungs, Gastrointestinal, Ears / Nose / Throat, Extremities, and Skin) will be assessed at the Screening Visit.

7.1.1 Study Specific Procedures

In addition to the regular standard of clinical care, the following study specific procedures will be included as part of the study.

Past medical history of and previous treatment of head lice must be recorded irrespective of the term it was given. Corresponding condition shall be captured in the subject's Medical History.

Visual Assessment of Head Lice:

Subjects and their household members will be thoroughly assessed for a minimum of 15 minutes for the presence or absence of live head lice, including adult lice, nymphs, and nits. Results will be recorded on the Site Assessment form.

Skin/Scalp Irritation Assessment:

Subjects will be assessed for skin and scalp pruritus, erythema, excoriation, and pyoderma. Results will be recorded on the Site Assessment form.

Ocular Irritation:

Subjects will be assessed for eye irritation, conjunctivitis, and ocular hyperemia. Results will be recorded on the Site Assessment form.

Subject Diary:

Administration of a checklist for laundry disinfection measures, application and removal of the study drug for index subject. Subject Assessments:

Administration of questionnaires for subject-reported outcomes. The site will provide a Subject Self-Assessment Worksheet to record the grading of Itching and Stinging/Burning sensations. Analysis of tolerability will be based on scoring scales of Stinging/Burning and Itching sensations collected during Subject Self-Assessment at all follow-up visits between the test and reference treatment groups.

7.2 Laboratory Procedures/Evaluations

7.2.1 Clinical Laboratory Evaluations

A urine pregnancy test will be performed for females of childbearing potential, this includes index subjects. The baseline result must be available and must be negative before the index subject can apply the study drug. A positive pregnancy test will disqualify the entire household from participation in the study.

7.3 Study Schedule

7.3.1 Screening

Screening Visit Day -1 to 0 (Visit 1)

- Obtain informed consent of potential participant verified by signature on written informed consent for screening form.
- Record demographic information, obtain medical history, alcohol and tobacco use, and history of head lice.

- Review medications history and concomitant/prohibited medications to determine eligibility based on inclusion/exclusion criteria.
- Verify inclusion/exclusion criteria.
- Perform medical examinations needed to determine eligibility based on inclusion/exclusion criteria.
- Collect urine sample for pregnancy testing for all index subjects of child bearing potential.
- Perform assessment for living head lice on index subjects and household members for a minimum of 15 minutes.
 The index subject must be the youngest family member presenting with at least 3 live lice. After the index subject
 has been identified, additional infested household members will also be assessed for infestation (up to 3 per
 household).
- Household members must have an active head lice infestation defined as: At least 1 live louse (adult and/or nymph) present on the scalp and/or hair, as determined by a trained evaluator (with the exception of the male head of household who may self-assess as being lice free).
- Schedule study visits for participants who are eligible and available for the duration of the study.

7.3.2 Enrollment/Baseline

Enrollment/Baseline Visit Day 1 (Visit 1/ Visit 2)

- Review concomitant and prohibited medications.
- Record vital signs, results of examinations, other assessments.
- Perform assessment for living head lice on index subject and household members (up to 3 per household) for visual confirmation of infestation for a minimum of 15 minutes.
- Provide Standard of Care treatment on-site to infested household members (up to 3 per household).
- Randomize the index subject.
- Provide the study treatment for index subject.
- Provide index subject with subject diary and homecare instructions.
- Record Subject Self-Assessment for index subjects.
- Inform index subject when to come back for their first follow-up visit.

7.3.3 Follow-up

Follow-up Visit Day 2 (Visit 3) (+/- 1 Day)

- Record adverse events as reported by participant or observed by investigator.
- Collect used test tube product from index subject.
- Concomitant and prohibited medication review.
- Perform assessment for living head lice on index subject for visual confirmation of infestation for a minimum of 15 minutes.
- If active lice are present on index subject, provide Standard of Care and withdraw the subject from the study.
- Record Subject Self-Assessment for index subjects.
- Perform skin/scalp irritation and ocular irritation for index subjects and record results on Site Assessment form.
- Record index subject's adherence to treatment program through collection of subject diary.
- Inform index subject when to come back for their follow-up visit.

Follow-up Visit Day 8 (Visit 4) (+/- 2 day)

- Record adverse events as reported by participant or observed by investigator.
- Concomitant and prohibited medication review.
- Perform assessment for living head lice on index subject for visual confirmation of infestation for a minimum
 of 15 minutes.
- If active lice are present, provide Standard of Care and withdraw the subject from the study.
- Record Subject Self-Assessment for index subjects.
- Perform skin/scalp irritation and ocular irritation for index subjects and record results on Site Assessment form.
- Inform index subject when to come back for their final study visit.

7.3.4 Final Study Visit

Final Study Visit Day 15 (Visit 5) (+/- 3 days)

- Record adverse events as reported by participant or observed by investigator.
- Perform vital signs, results of examinations, and other assessments.
- Concomitant and prohibited medication review.
- Collect urine sample for pregnancy testing for any index subject of child bearing potential.
- Perform assessment for living head lice on index subject for visual confirmation of infestation for a minimum of 15 minutes.
- Record Subject Self-Assessment for index subjects.
- Perform skin/scalp irritation and ocular irritation for index subjects and record results on Site Assessment form.
- Provide rescue standard of care treatment for any index subjects requiring additional treatment.

7.3.5 Unscheduled Visit

Subjects will be encouraged to report any complications or adverse effects during their participation. Investigator may evaluate the subject at an unscheduled visit, if subject's condition is considered to be worsening.

7.3.6 Rescreening

If for some reason a subject is approved to participate in the study, but cannot return to the clinical site within 24 hours of their screening visit, they may be rescreened within 1 week. This rescreening may also occur if all household members cannot be assessed at the clinical site within 24 hours of the index subject's approval to participate in the study. Rescreening will be considered on an individual subject basis and must first be approved by the Investigator or Medical Monitor.

7.4 Concomitant Medications, Treatments, and Procedures

All medications (both prescription and nonprescription, and including vitamins, herbals, topical, inhaled, and intranasal) taken within 30 days prior to the start of the Study Drug and through the final study visit will be recorded on the appropriate eCRF (using their generic and brand names, if known) with the corresponding indication, start and stop dates. At each study visit, subjects will be asked whether they have started or discontinued any medication since their previous study visit. This includes single use or PRN (as needed) medication use.

Protocol Number: MAP-7189

Version 1.3; 28 December 2017

Previous treatment of head lice must be recorded irrespective of the term it was given. Corresponding condition shall be captured in the subject's Medical History.

7.4.1 Precautionary Medications, Treatments, and Procedures

In previous studies for topical Ivermectin, no exploration of drug-drug interactions was performed.

7.5 Prohibited Medications, Treatments, and Procedures

Head lice treatment products (over the counter [OTC], home remedy and/or Prescription) are prohibited 15 days prior to and during the study. These include, but are not limited to:

- Nix
- Rid
- Kwell
- LiceMD

7.6 Rescue Medications, Treatments, and Procedures

If live lice are present on Day 2, Day 8 or Day 15, the subject will receive an over-the-counter (OTC) rescue treatment for head lice and their study participation will be considered complete and will be considered a treatment failure, with subjects to be considered in both the mITT and PP population.

7.7 Participant Access to Study Drug at Study Center

Participants will receive the study medication at their Enrollment/Baseline Visit.

8 Assessment of Safety

8.1 Specification of Study Parameters

The Investigator will monitor each subject for clinical evidence of adverse events on a routine basis throughout the study. The Investigator will assess and record any AE in detail including the date of onset, description, severity, time course, duration and outcome, relationship of the adverse event to study drug, an alternate etiology for events not considered "related" or "probably related" to study drug, final diagnosis, if known, and any action(s) taken. For AEs to be considered intermittent, the events must be of similar nature and severity and each intermittent AE will be reported separately. AEs and SAEs, whether in response to a query, observed by site personnel, or reported spontaneously by the subject will be recorded, monitored and followed-up until the resolution (or until the Investigator deems the event to be stable/chronic).

8.1.1 Definition of Adverse Events (AE)

An AE is defined as any untoward medical occurrence in a patient or clinical investigation subject administered a pharmaceutical product and which does not necessarily have a causal relationship with this treatment. An AE can

therefore be any unfavorable and unintended sign (including an abnormal laboratory finding), symptom, or disease temporally associated with the use of a medicinal (investigational) product, whether or not the event is considered causally related to the use of the investigational product. Treatment-emergent AEs (TEAE) will include any AEs reported beginning with the first application of study drug on Day 1.

Such an event can result from use of the drug as stipulated in the protocol or labeling, as well as from accidental or intentional overdose, drug abuse, or drug withdrawal. Any worsening of a pre-existing condition or illness is considered an AE. I.e., if a new signs or symptom or worsening of a sign or symptom was believed by the investigator to be related to the study drug and not the disease, then it was recorded as an AE. Clinically significant abnormalities are to be followed to resolution (i.e. become stable, return to normal, return to baseline, or become explainable). Changes in vital signs are considered to be AEs only if they necessitate therapeutic medical intervention, and/or if the Investigator considers them to be AEs.

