8.2.2 Relationship to Study Drug

The Investigator will use the following definitions to assess the relationship of the AE/SAE to the use of investigational product:

Definitely Related The event occurred within a reasonable time after drug administration or drug

concentration and body fluids demonstrated that the study drug was present: the event could not be reasonably explained by known characteristics including concomitant

therapies; the adverse event abated after discontinuing the study drug.

Probably Related The event has a strong temporal relationship to study drug or recurs on re-challenge and

another etiology is unlikely or significantly less likely.

Possibly Related The event has a strong temporal relationship to the study drug and an alternative etiology

is equally or less likely compared to the potential relationship to study drug.

Probably Not Related The event has little or no temporal relationship to the study drug and/or a more likely

alternative etiology exists.

Not Related The event is due to an underlying or concurrent illness or effect of another drug and is not

related to the study drug (e.g., has no temporal relationship to study drug or has a much

more likely alternative etiology).

If an Investigator's opinion of not related to study drug is given, an alternate etiology must be provided by the Investigator for the AE.

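### Protocol 8.1.1 defines an adverse event regardless of cause, then implies that new or worsening signs and symptoms are recorded when judged drug-related; the two rules need reconciling

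*Protocol*

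**What the plan says.** The first paragraph of Protocol 8.1.1 counts an untoward occurrence as an AE "whether or not the event is considered causally related to the use of the investigational product". The second paragraph adds, again with no causality condition: "Any worsening of a pre-existing condition or illness is considered an AE".

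The next sentence opens with an i.e. and so presents itself as what the preceding text means in practice. It takes in both new and worsening signs and symptoms, and sets this condition: "was believed by the investigator to be related to the study drug and not the disease, then it was recorded as an AE".

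The general recording rule in Protocol 8.1 has no such condition: "AEs and SAEs, whether in response to a query, observed by site personnel, or reported spontaneously by the subject will be recorded". The causality scale in Protocol 8.2.2 has five grades, two of them on the unrelated side. The last begins "Not Related The event is due to an underlying or concurrent illness", and the section closes with an instruction for that grade: "If an Investigator's opinion of not related to study drug is given, an alternate etiology must be provided by the Investigator for the AE".

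**The concern.** A site reading 8.1.1 for its working rule could take the explanatory sentence as the test for opening an AE record. It would then apply its own causality judgement before the event reaches the database, instead of recording the event and grading causality afterwards. Two sites could each believe they were following the protocol and record different events.

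AEs are the stated variable for the safety endpoints (Protocol 10.4.3, SAP 5.4), and safety of Test relative to Reference is part of the secondary objective (Protocol section 3, SAP section 2). The two active lotions have largely different inactive ingredients (Protocol 6.1.2), so local reactions are a real question. They are also the events most easily attributed to the infestation. An event that is never recorded leaves no AE record to recover at analysis.

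**Working it through.** The documents give no figure that depends on this point, so the check is mainly a comparison of texts.

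**1. What the sentence covers.** It names new signs or symptoms as well as worsening ones, so it goes beyond the pre-existing conditions mentioned just before it. It is limited to signs and symptoms. It does not mention intercurrent diseases, and vital signs have their own rule later in the paragraph.

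**2. Whether it restricts recording.** It is worded as an if, not an only-if, so the restriction is implied. The implication is still strong: the sentence is offered as the meaning of the definition, and its condition would serve no purpose if unrelated signs and symptoms were to be recorded anyway.

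**3. The other provisions, side by side.**

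| Place | Rule | Does recording depend on causality? |
|---|---|---|
| Protocol 8.1.1, definition | Untoward occurrence, any cause | No |
| Protocol 8.1.1, explanatory sentence | New or worsening sign or symptom | Yes, by implication |
| Protocol 8.1 | AEs recorded from any source, with relationship and, where not considered related, an alternative cause | No |
| Protocol 8.2.2 | Two unrelated grades; alternative cause required for the last | No |
| Protocol 8.4.2 | SAEs reported whether or not related | No |
| SAP 3.4.3 | Treatment-emergent AE defined by timing alone | No |
| SAP section 8 | All treatment-emergent AEs (Table 28) kept apart from possibly or probably related ones (Table 30) | No |

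One provision points one way and the rest point the other. None states an order of precedence.

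**4. What the separate scores recover.** Pruritus, erythema, excoriation, pyoderma and ocular signs are scored by site staff at Days 2, 8 and 15. Itching and stinging/burning are self-rated from Baseline (Protocol 7.1.1 and 16.1). None of these depends on causality. Their limits are:
- Self-ratings cover the last 24 hours (SAP 5.3), so a reaction between visits can be missed.
- Tolerability is tabulated for the mITT and PP populations (SAP 5.3), not the Safety population.
- The schedule has no scalp-irritation score at Visit 2, although SAP 5.3 expects one, so worsening from baseline of the site-rated signs cannot be reconstructed.
- Events away from the scalp and eyes, such as headache or nausea, have no substitute score.

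**5. Illustration only: how sensitive the AE tables would be.** The Protocol Synopsis describes AEs that occur in at least 5% of subjects. Assume the threshold applies per arm and use the planned arm sizes in Protocol 10.5 (120 per active arm, 40 on placebo). The count needed is r = ceil(0.05 × 120) = 6, or ceil(0.05 × 40) = 2. With true incidence p and recorded share s of affected subjects, both assumed, the chance of reaching the threshold is P(X ≥ r) with X ~ Binomial(n, p·s).

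| n (r) | p | s = 1 | s = 0.75 | s = 0.5 | s = 0.25 |
|---|---|---|---|---|---|
| 120 (6) | 5% | 0.558 | 0.295 | 0.081 | 0.004 |
| 120 (6) | 8% | 0.925 | 0.732 | 0.348 | 0.034 |
| 120 (6) | 10% | 0.984 | 0.894 | 0.558 | 0.081 |
| 40 (2) | 5% | 0.601 | 0.445 | 0.264 | 0.089 |
| 40 (2) | 8% | 0.841 | 0.701 | 0.479 | 0.190 |
| 40 (2) | 10% | 0.920 | 0.812 | 0.601 | 0.264 |

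If s is the same in both active arms, a true difference d in incidence appears as s·d. For example, 10% against 5% with s = 0.5 appears as 5% against 2.5%, so a gap of 5 points becomes 2.5. The documents supply neither p nor s; the table shows direction and sensitivity and is not an estimate.

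**The case against.** The best defence is that the sentence is clumsy but harmless. It does not say only if, whereas the same paragraph does use that wording for vital signs. Its contrast between drug and disease can be read as an attempt to separate drug effects from signs of the infestation. Its past tense fits poorly as an instruction to sites. The rest of the protocol points to broad recording, and even the subject diary (Protocol 16.2) asks about health problems with no causality filter. A site working from those sections would record unrelated AEs.

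Much of this stands. Under-recording is a possibility that depends on which text a site follows. Safety reporting is descriptive, causality is judged under the blind, and events judged drug-related are recorded on either reading. The defence does not remove the contradiction: new signs and symptoms are expressly covered, and no provision settles which rule prevails.

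Three stronger readings are tempting, and the documents do not support them:
- A reader might infer that the two unrelated grades in 8.2.2 could never be used. Unrelated diseases, vital-sign AEs and SAEs could still be graded there, because the sentence covers signs and symptoms only.
- A reader might infer that reported AE incidence falls by the share of events judged unrelated. The documents give no such share. Subject-level incidence also need not fall in step with event counts, since a subject with one related and one unrelated event is still counted.
- A reader might infer that itching, erythema and excoriation would be lost altogether. They are scored at the scheduled follow-up visits whatever their presumed cause.

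**Conclusion.** The contradiction is in the current text and should be corrected. The explanatory sentence in 8.1.1 conflicts with the definition it claims to explain, with Protocol 8.1, 8.2.2 and 8.4.2, and with SAP 3.4.3 and the table list in SAP section 8. If sites follow it, non-serious signs and symptoms judged unrelated could be under-recorded, unevenly between sites. That conclusion assumes at least some sites treat the sentence as operative, which the documents neither establish nor rule out. The size of the loss cannot be derived.

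The scheduled scores mitigate the problem for local scalp and ocular signs only. SAE reporting is protected by 8.4.2, although 8.1.2 defines an SAE as an AE that meets further criteria, so clarity upstream helps there too. The primary endpoint is unaffected. What is exposed is the main safety variable of the secondary objective, which makes this a correction worth making and not a threat to the trial's main conclusion.

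**What to change.** Delete the explanatory sentence in 8.1.1. Alternatively, reconcile it with the first paragraph by replacing it with text such as: *AEs as defined above are recorded regardless of the investigator's view of causality, which is rated separately under 8.2.2.* Leave the existing vital-signs rule unchanged.

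Tying the replacement to the existing definition is deliberate. A blanket rule that any new sign or any worsening from baseline is an AE would clash with the vital-signs rule. It could also turn each one-point rise in an itching score into an AE.

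The cost is a one-sentence protocol change, a note to sites so that all apply the same rule, and somewhat more AEs to record. The SAP's definitions and tables need no change, because they already assume broad recording.
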